4.2.4.10 FVC and FEF25-75

Summary statistics, including N, mean SD, median and range will also be presented for each treatment group at each visit.

4.2.4.11 Night time awakenings

Weekly mean number (percentage) of nights with awakening due to asthma will be summarised by descriptive statistics including N, mean, SD, median, and range.

4.2.4.12 Data collected at Sentinel Dosing procedures

Efficacy data collected during the sentinel dosing procedure (IC, FEV₁/FVC ratio, PEF, DLco, FeNO, Forced Expiratory Flow 25%, Forced Expiratory Flow 75%, Forced Expiratory Flow 25% to 75% (FEF25-75%), FEV₁ and VC) at timepoints 0.5, 1,2, 6, 12 and 24 hours will not be included in descriptive summaries or any statistical analysis. This data will be listed only.

4.2.5 Safety analysis

All safety variables will be summarized by treatment received and evaluated descriptively utilizing the safety analysis set. No formal hypothesis testing of safety data is planned.

4.2.5.1 Adverse events

All AEs recorded in the eCRF will be coded according to the terminology of the latest version of MedDRA. AEs may be based on signs and symptoms or may be based on examinations and tests as described in Sections 6.3.5 and 6.3.6 of the protocol respectively.

An overall summary table will be produced showing the number and percentage of subjects with at least 1 AE in any of the following categories: AE, serious adverse events (SAEs), deaths due to AE and AEs causing discontinuation of IP (DAEs). The total number of AEs in the different AE categories in terms of AE counts will also be presented (i.e., accounting for multiple occurrences of the same event in a subject).

AEs will be summarised by SOC and PT. For each PT, the number and percentage of subjects reporting at least one occurrence will be presented i.e. for a subject multiple occurrences of an AE will only be counted once.

AEs (by PT) will be summarised by causality and maximum intensity. If a subject reports multiple occurrences of the same AE, the maximum intensity will be taken as the highest recorded maximum intensity (the order being mild, moderate and severe). A missing intensity will be considered as severe and a missing causal relationship to IP will be considered as related.

The following will also be summarised by SOC and PT: SAEs; DAEs; most common AE's (frequency of >5%) (by PT only); and AEs with outcome of deaths.

Treatment-emergent AEs will be tabulated (number and percentage of patients) by system organ class, preferred term (PT), intensity, and relation to IP according to the treatment actually received.

Adverse events will be summarized separately for the following periods: AEs occurring during pre-treatment, AEs occurring during study, AEs occurring during ICS+LABA treatment period, AEs occurring during ICS taper down period and AEs occurring during remainder of study as defined in [Section 3.4.1](#).

Summary tables will also be produced showing Flu-like Adverse Events by preferred term, relationship to treatment and severity. The number and percentage of subjects with at least 1

Flu-like AE will be displayed as well as the total number of AEs for each preferred term by maximum reported intensity. Separate tables will be presented for each of the following periods: AEs occurring during study, AEs occurring during ICS+LABA treatment period, AEs occurring during ICS taper down period and AEs occurring during remainder of study as defined in [Section 3.4.1](#). A table will also be presented for the AEs occurring during IP only treatment period. This is defined as

- *AEs occurring during IP only treatment period (onset date \geq Visit 11 (Week 9) < Visit 15 (Week 13))*

Flu-like symptoms are defined as events of arthralgia, chills, pyrexia (fever), or myalgia (see section 6.1.1 of protocol).

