8.2 Sample size estimate

This trial has about 90% power to yield a statistically significant ($\alpha = 0.05$, 2-sided) difference between the pooled active and placebo groups in time to loss of asthma control given that the cumulative number of controlled subjects at week 52 is 20% and 60% for control versus active respectively. Assuming a drop-out of about 10-15%, this will require about 70 patients in total (32 events).

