8.5.4 Analysis of the primary variable (s)

The primary efficacy variable is the time to loss of asthma control, and the primary analysis is to compare the time to loss of asthma control for AZD1419 with placebo. The Time to loss of control in the AZD1419 group will be compared to that of the placebo group using a log rank test (with accompanying Kaplan-Meier plot)

The hypothesis test will be one-sided, with $\alpha=0.05$.

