1.2 Study design

This is a randomised, double blind, placebo-controlled Phase 2a study designed to assess the efficacy and safety of 13 once weekly doses of inhaled AZD1419 administered to patients with eosinophilic asthma controlled on a maintenance treatment of Inhaled Corticosteroids (ICS) plus a Long-acting Beta Agonist(s) LABA but no other controller medication.

This study is a multi-centre study conducted at 16 centres in 4 countries.

Prior to randomisation patients will undergo an approximately 2-4 weeks screening period. Eligible patients will be prescribed their usual controller medication (i.e. ICS + LABA in separate inhalers, in addition to a rescue medication inhaler (short-acting B2 agonist [SABA]), and issued electronic diaries, peak flow and FeNO meters to record asthma symptoms and lung function during each morning and evening at home. Asthma control will be assessed using the 5-item asthma control (ACQ-5) and when patients have shown to be controlled (ACQ-5 ≤ 0.75) they are randomised to receive AZD1419 or placebo administered as an inhalation at the clinic once per week.

A withdrawal design will be used where the first 6 doses of investigational product (IP) will be administered as add-on to the patient's regular ICS + LABA medication. The controller

medication will then be tapered down and discontinued during the next 3 doses of IP, and the last 4 doses will be administered during a period of complete ICS and LABA withdrawal (see [Figure 1](#)). In addition the study drug dose level will be adjusted using an adaptive dosing scheme (defined in [Section 4.2.2](#) of the protocol) based on appearance of flu-like symptoms. The primary endpoint is loss of asthma control, defined in [Section 1.1.1](#). When a patient meets the primary endpoint, the patient will resume ICS + LABA and will be followed for an additional 4 weeks before discontinuing the study.

The total duration of patient participation will be up to 56 weeks. Prior to randomisation patients will undergo an approximately 2-4 week screening period, which is then followed by a 12 week dosing period and an up to 40 week observation period following the last dose. The study design is presented in [Figure 1](#). The schedule of trial procedures is presented in Table 1 of the CSP.

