3.4.1 Adverse events

The definitions of adverse events (AEs) and serious adverse events (SAEs) are given in Sections 6.1 and 6.2 of the CSP.

All AEs recorded in the eCRF will be coded according to the terminology of the latest version of the Medical Dictionary for Regulatory Activities (MedDRA).

All adverse events will be listed for each patient and summarised by treatment actually received. Treatment-emergent AEs will be tabulated (number and percentage of patients) by system organ class (SOC), preferred term (PT), intensity and relation to study medication.

Any AE occurring before the start of study treatment will be included in the data listings but will not be included in the summary tables of AEs and excluded from safety analysis set.

If an AE has a missing onset date then unless the stop date of the AE indicates otherwise, this will be considered 'on-treatment'. Similarly, if an AE has a partial onset date, then unless the partial onset date or the stop date indicates otherwise, this will be considered 'on-treatment'.

AE data will be categorized according to their onset date into the following periods:

- AEs starting during pre-treatment (onset date \geq Visit 1 (Week -4) and before the first dose of IP)
- AEs starting during study (onset date \geq the first day of IP and \leq Visit 21 (Week 52))
- AEs starting during ICS + LABA treatment period (onset date \geq the first day of IP and $<$ Visit8 (Week 6))
- AEs starting during ICS taper down period (onset date \geq Visit 8 (Week 6) and $<$ Visit 11 (Week 9))
- AEs starting during remainder of study (onset date \geq Visit 11 (Week 9) \leq Visit 21 (Week 52))

The timing of AEs will be assigned to the period in which they first started. The same during treatment definition will be used for laboratory and physical examination data, where applicable. Note, not all Exacerbations will be recorded as AEs.

Common AEs, AEs with outcome of death, SAE, DAEs and Flu-like AEs will be summarized separately. Flu-like AEs are defined in [Section 4.2.5.1](#).

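### Adverse events are compared as crude percentages although time in study depends on the primary outcome, which may inflate background-AE percentages in the arm that keeps control longer, mainly after Week 9

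*SAP*

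**What the plan says.** **Follow-up.** On meeting the primary endpoint a patient resumes ICS+LABA and "will be followed for an additional 4 weeks before discontinuing the study" (SAP 1.2; Protocol 1.4 agrees). Protocol 4.3 adds that IMP is stopped. Patients who keep control are followed to Week 52. AEs are collected from randomisation through follow-up (Protocol 6.3.1).

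**AE summaries.** "Treatment-emergent AEs will be tabulated (number and percentage of patients) by system organ class" (SAP 4.2.5.1). Total AE counts are also shown. Neither SAP 3.4.1 nor 4.2.5.1 plans patient-time, an exposure-adjusted rate or time to first AE. The extent-of-exposure summary (SAP 4.2.3.1) covers IP days only, so it does not show time at risk for AEs.

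**Periods.** SAP 3.4.1 sorts AEs by onset date against visits: ICS+LABA (before Visit 8), taper (Visit 8 to before Visit 11), and "AEs starting during remainder of study" (Visit 11 to Visit 21). For flu-like AEs, "A table will also be presented for the AEs occurring during IP only treatment period", defined as Visit 11 to before Visit 15. No period closes when a patient loses control or resumes ICS+LABA.

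**Status.** Safety is descriptive, with no formal testing (SAP 4.2.5).

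**The concern.** A crude percentage compares arms fairly only if patients are observed for similar lengths of time. Here the length of observation is set by the efficacy outcome. If AZD1419 prolongs control, its patients are watched for longer and have more time to report colds, headaches and other events unrelated to treatment. Equal risk per unit of time would then appear as more AEs on AZD1419. Raw event counts have the same weakness. The distortion would be present when the trial succeeds, which is when the safety profile will be read most closely.

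A second, separate matter is labelling. A patient who is back on ICS+LABA and off IMP is still counted under the taper, IP-only or remainder period, although those labels describe a different treatment state.

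**Working it through.** **Inputs from the documents.** Protocol 8.2 assumes that the "cumulative number of controlled subjects at week 52 is 20% and 60% for control versus active respectively". Loss of control can count at any time during the taper or later (Protocol 4.3), and LABA stops just before dose 7 at Visit 8, which is Week 6 (Protocol 4.2). Follow-up after loss of control is 4 weeks, and the maximum is 52 weeks.

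**The plan's own figure first.** HR = ln(0.60)/ln(0.20) = 0.317. Schoenfeld events for 90% power at two-sided 0.05 with 1:1 allocation: 4(1.960 + 1.282)²/(ln 0.317)² = 31.9, that is 32 events with 90.1% power. This matches the stated 32 events and about 90%, so the 20% and 60% are used here as the plan uses them.

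**Assumptions of this check.** Loss of control is exponential from Week 6, there is no other dropout, and the AE hazard is constant and equal in both arms. The documents give no AE rate, so 0.5, 1 and 2 per patient-year are used.

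**Step 1, hazard of losing control.** λ = −ln S(52)/46.
- Placebo: 1.609/46 = 0.03499 per week.
- AZD1419: 0.511/46 = 0.01110 per week.

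**Step 2, time in study.** With X = min(T + 4, 52), the mean is 10 + (1 − e^(−42λ))/λ.
- Placebo: 10 + 0.770/0.03499 = 32.0 weeks.
- AZD1419: 10 + 0.373/0.01110 = 43.6 weeks. The ratio is 1.36.
- Every X is at least 10 weeks, so time after Week 9 is 9 weeks less: 23.0 v 34.6 weeks.

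**Step 3, crude percentage with any AE.** With weekly AE hazard h = rate/52, P0 = 1 − e^(−10h) × A, where A = [λ/(λ+h)](1 − e^(−42(λ+h))) + e^(−42(λ+h)). For the remainder period, e^(−h) replaces e^(−10h). At 1 per year (h = 0.01923):
- Placebo: A = 0.682, P0 = 1 − 0.825 × 0.682 = 44%.
- AZD1419: A = 0.543, P0 = 1 − 0.825 × 0.543 = 55%.

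| AE rate per patient-year, equal in both arms | Whole study, placebo v AZD1419 | Remainder, placebo v AZD1419 |
|---|---|---|
| 0.5 | 26% v 34% | 19% v 28% |
| 1 | 44% v 55% | 33% v 47% |
| 2 | 66% v 78% | 52% v 69% |

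Events per patient-year would show a ratio of 1.00 in every row, by construction.

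**Step 4, early periods.** Mean time is 6.0 weeks in both arms for Weeks 0-6 and 3.0 weeks in both arms for Weeks 6-9, so those tables show no gap under these assumptions.

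**Step 5, other starting point.** If loss of control could begin at randomisation, mean time is 29.0 v 42.3 weeks. At 1 per year the crude figures are then 40% v 54% overall and 29% v 45% in the remainder period. Week 6 fits Protocol 4.3 better. Across both starting points and 0.5 to 2 per year, the gap is 8 to 16 points overall and 9 to 21 points after Week 9.

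**Step 6, losses of control recorded as AEs.** SAP 3.4.1 notes that not every exacerbation will be recorded as an AE, which implies that some will be. If a share q of losses of control is recorded, the percentage with any AE is (1 − q)P0 + qP1, with P1 = 1 − S(52)e^(−52h). At 1 per year P1 is 92.6% v 77.9%, and the arms are equal at q = 11.4/(48.9 − 22.8) = 0.44. At 0.5 per year they are equal at about q = 0.25, and at 2 per year at about q = 0.69. Above these values placebo looks worse.

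**Step 7, resumed controllers.** With loss of control from Week 6, the share of patient-time spent back on ICS+LABA is 13% on placebo v 4% on AZD1419 in both the remainder and IP-only windows, and 5% v 2% in the taper window.

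**The case against.** The strongest reply is that the direction is not fixed. A reader might infer that AZD1419 will look less safe. The documents do not support that. There is no expected difference in follow-up if the drug has no effect, and step 6 shows that asthma events recorded as AEs can cancel or reverse the gap. This stands, and limits the point to background AEs under a working drug. It does not rescue the crude comparison, which would then mix follow-up time with efficacy failure in unknown proportion.

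A reader might also infer that ignoring resumed controllers drives the bias. It does not. AEs after resumption arise mainly on placebo (13% v 4% of remainder patient-time), so counting them works against the gap. That is a labelling defect only, and the IP-only table concerns flu-like AEs alone.

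Other mitigations are real but partial:
- Safety is descriptive.
- Kaplan-Meier plots of IP discontinuation, study withdrawal (SAP 4.2.1) and loss of control (SAP 4.2.4) will make unequal follow-up visible, but they adjust no AE table.
- AEs are also tabulated by relation to IP, and the early-period tables are close to balanced.
- AE reporting may be denser during weekly dosing. At 1 per year, doubling the hazard in Weeks 0-12 cuts the overall gap from 11 to 9 points and quadrupling it cuts it to 6. The remainder gap survives.
- The denominator for period percentages is not written in SAP 4.2.5.1. All patients in the arm is an inference from SAP 2.1.3, which bases every safety summary on the safety set.

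**Conclusion.** The point holds in a limited form. The plan makes follow-up depend on the primary outcome and offers only crude percentages and raw counts for AEs. If the drug performs as the sample size assumes, background-AE percentages may be inflated on AZD1419 by about 8 to 12 points over the whole study and about 9 to 17 points after Week 9. This rests on an equal, constant AE rate of 0.5 to 2 per patient-year, exponential loss of control from Week 6 and no other dropout. The rate is an assumption, since the documents give none.

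It would be too strong to say that the whole safety objective is confounded with efficacy: the tables for Weeks 0-6 and 6-9 are little affected, and the sign of the overall gap depends on how many losses of control are recorded as AEs. The planned during-study and remainder comparisons can nevertheless mislead, and the correction is cheap, so it should be made.

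**What to change.** In SAP 4.2.5.1, for the during-study and remainder-of-study tables, keep the crude percentages and add for each arm:
- total patient-time in study;
- patients with event per 100 patient-years, with time counted to first event or end of follow-up;
- events per 100 patient-years.

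Restricting denominators to patients still in study at the start of a period is not enough: with loss of control from Week 6, every patient in the check above is still in study at Week 9. If the AE hazard is higher during dosing, a whole-study rate is diluted in the arm followed longer, so the remainder-period rate should be read beside it.

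As a separate labelling correction, show AEs that start after ICS+LABA is resumed in their own column, and not under the taper, IP-only (flu-like AEs) or remainder periods.

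Treatment and follow-up do not change, and no new data appear to be needed: AE onset dates, the loss-of-control date and maintenance medication use are already recorded (Protocol 6.3.3 and 5.1.2; SAP 3.2). The downside is a few extra columns in a descriptive safety summary.

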4.2.2 Dose Adaptation Procedure

Given the well-known potential for flu-like symptoms from TLR9 agonism, dosing for each patient will be adapted based on the individual's flu-like AEs. The flu-like symptoms usually respond well to paracetamol (and otherwise resolve spontaneously within 24-48 hours following dosing), and the dose adaptation should be based on the assessment of flu-like symptoms after intake of paracetamol.

After the first 4 doses an assessment of the individual patient will be performed according to experiences of flu-like AEs (arthralgia, chills, pyrexia, myalgia) within 24h of inhalation, with adaptation of AZD1419 accordingly:

If no or only mild flu-like AEs occur after the first 4 doses, then the subsequent doses will be stepped up to 8 mg.

If any severe flu-like AEs occur after any of the first 4 doses, then the subsequent doses will be stepped down to 1 mg.

Otherwise, the subsequent doses will be maintained at 4 mg.

All patients will continue dosing with placebo or AZD1419 at the adjusted levels until they have received a total of 13 inhaled weekly doses.

[figure not shown]
All dosing decisions are subject to investigator judgment. If an investigator believes that a patient is not tolerating a dose for any reason, the next dose can be reduced independent of the rules described above.

Dosing will be stopped in patients who do not tolerate a 1mg dose and they will be followed for an additional 4 weeks for safety before they discontinue the study.

Since e.g. side effects from influenza vaccination could potentially impact the interpretation of the flu-like symptoms after the dosing of study drug, it is suggested that such vaccination should be performed e.g. 2 days after a dose of IMP.

For definition of severity of AE (including flu-like symptoms), see Section 6.3.3.

Figure 2 Dosing

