6.1.1 Definition of Flu-like Symptoms

For the dose adaptation in the present study flu-like symptoms are defined as events of arthralgia, chills, pyrexia (fever), or myalgia, any of which occur within 24 hours after treatment with IP. The severity of these flu-like symptoms are defined as mild, moderate and severe in accordance with the general AE definitions described below (Section [6.3.3](#)), and should for the purpose of dose adaptation be graded with regards to severity after intake of e.g. paracetamol. The individual symptoms should be reported, i.e. not reported as the preferred term "Influenza-like illness".

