6.3.3 Variables

The following variables will be collect for each AE;

- AE (verbatim)
- The date and time when the AE started and stopped
- Maximum intensity of the adverse event
Intensity rating scale:
1 mild (awareness of sign or symptom, but easily tolerated)
2 moderate (discomfort sufficient to cause interference with normal activities)
3 severe (incapacitating, with inability to perform normal activities)
- Whether the AE is serious or not
- Investigator causality rating against the Investigational Product (yes or no)
- Action taken with regard to investigational product
- Outcome.

In addition, the following variables will be collected for SAEs:

- Date AE met criteria for serious AE
- Date Investigator became aware of serious AE
- AE is serious due to
- Date of hospitalization
- Date of discharge
- Probable cause of death
- Date of death
- Autopsy performed
- Causality assessment in relation to Study procedure(s)
- Description of AE. It is important to distinguish between serious and severe AEs. Severity is a measure of intensity whereas seriousness is defined by the criteria in Section 6.2. An AE of severe intensity need not necessarily be considered serious. For example, nausea that persists for several hours may be considered severe nausea, but not a SAE unless it meets the criteria shown in Section 6.2. On the other hand, a stroke that results in only a limited degree of disability may be considered a mild stroke but would be a SAE when it satisfies the criteria shown in Section 6.2.

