4.2.3 Exposure and Compliance

Extent of exposure to IP by compliance, total treatment duration by mean daily dose, and recordings on eDiary will be summarized by treatment group and using both the safety analysis set and full analysis set.

The date and time of all IP administrations, and all missed doses will be listed using the safety analysis set.

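### The SAP's flu-like AE tables leave out the protocol's 24-hour post-dose window and never separate doses 1-4 from the adapted doses, so they can dilute or distort the post-dose reaction

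*SAP*

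**What the plan says.** Protocol 6.1.1 names four terms and ties them to the adaptation: "For the dose adaptation in the present study flu-like symptoms are defined as events of arthralgia, chills, pyrexia (fever), or myalgia". It then sets a limit on when they must start: "any of which occur within 24 hours after treatment with IP". Protocol 4.2.2 uses the same condition when the dose is reviewed after dose 4: "within 24h of inhalation, with adaptation of AZD1419 accordingly". Section 6.1.1 also says that severity "should for the purpose of dose adaptation be graded with regards to severity after intake of e.g. paracetamol".

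SAP 4.2.5.1 keeps the four terms and the cross-reference, but not the window: "Flu-like symptoms are defined as events of arthralgia, chills, pyrexia (fever), or myalgia (see section 6.1.1 of protocol". SAP 3.4.1 only points to 4.2.5.1.

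The SAP then plans flu-like tables by preferred term, relationship to treatment and severity, each for a calendar period:

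- during study: first dose to Visit 21 (Week 52);
- ICS+LABA: first dose to before Visit 8 (Week 6);
- ICS taper: Visit 8 to before Visit 11 (Week 9);
- "AEs starting during remainder of study": Visit 11 to Visit 21;
- IP only: Visit 11 to before Visit 15 (Week 13).

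None has a time-from-dose condition. SAP Section 6 has a general line on the categorisation of AE data, but nothing on the window.

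The data needed are recorded. Protocol 6.3.3 collects "The date and time when the AE started and stopped", and SAP 4.2.3 lists "The date and time of all IP administrations".

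**The concern.** Protocol 1.3 singles out flu-like events as the sensitive tolerability parameter, and the planned dose adaptation is built on them. A reader of the study report will expect the flu-like tables to show how often a dose provoked a reaction. Read literally, the SAP also counts fever or joint pain months after the last dose.

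Two features of the trial make this matter. Patients may be followed for 40 weeks after dosing ends. They also leave 4 weeks after loss of control (protocol 4.3), so the time in which background events can accrue may differ between arms.

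The protocol itself shows concern about background symptoms: 4.2.2 suggests giving influenza vaccination, for example, two days after a dose so that its side effects do not cloud the reading. Such side effects would fall outside the 24-hour window but inside the SAP's calendar periods.

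The ICS+LABA table also pools doses 1-4, given at one common level, with doses 5-6, given after adaptation. No planned flu-like table shows tolerability before and after the adaptation point.

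**Working it through.** The documents give no figure on this point, so there is none to reproduce.

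**1. Is the window applied?** SAP Table 6 puts Visit 14 (Week 12, dose 13) at target day 85 and Visit 15 at target day 99. Any event within 24 hours of doses 10-13 therefore starts between Visit 11 and Visit 15. With the window, the remainder-of-study and IP-only flu-like tables would contain the same events. Asking for both makes sense only if events after dosing are counted.

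**2. Share of each table inside the window.** With doses on days 1, 8, ..., 85, share = doses / days:

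| Table | Doses | Days | Share |
|---|---|---|---|
| During study (1-365) | 13 | 365 | 3.6% |
| ICS+LABA (1-42) | 6 | 42 | 14.3% |
| ICS taper (43-63) | 3 | 21 | 14.3% |
| Remainder (64-365) | 4 | 302 | 1.3% |
| IP only (64-98, or 64-91 if Week 13 is read as day 92) | 4 | 35 or 28 | 11.4% or 14.3% |

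For a patient followed to Week 52, 365 - 13 = 352 days (96.4%) of the during-study table lie outside the window.

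**3. Possible dilution.** Assume a background rate λ per patient-year for any of the four terms, a drug-reaction risk q on active only, and full follow-up in both arms. Then P(at least one event) = 1 - (1 - q)exp(-λt/365), with q = 0 on placebo. The values of λ and q are assumptions. Cells are placebo / active:

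| λ, q | 365 days | 91 days (dosing) | 13 days (window) |
|---|---|---|---|
| 0.1, 10% | 9.5% / 18.6% | 2.5% / 12.2% | 0.4% / 10.3% |
| 0.1, 30% | 9.5% / 36.7% | 2.5% / 31.7% | 0.4% / 30.2% |
| 0.5, 10% | 39.3% / 45.4% | 11.7% / 20.5% | 1.8% / 11.6% |
| 1.0, 10% | 63.2% / 66.9% | 22.1% / 29.9% | 3.5% / 13.1% |
| 1.0, 50% | 63.2% / 81.6% | 22.1% / 61.0% | 3.5% / 51.7% |

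The 91-day column stands for the three dosing-period tables together. The contrast nearly disappears over 365 days only when background is high and reactions are few. Over the dosing period it is diluted much less.

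**4. Unequal follow-up.** The sample-size section assumes 20% (placebo) and 60% (active) still controlled at Week 52. As a check on that input, the hazard ratio is ln 0.6 / ln 0.2 = 0.317, and 4(1.96 + 1.2816)² / (ln 0.317)² gives 32 events, the plan's own figure.

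Take an exponential time to loss of control, with exit 4 weeks later, capped at Week 52. If losses can start at week s, let T = 52 - s and h = -ln(S)/T. Mean follow-up is s + (1 - exp(-h(T - 4)))/h + 4:

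- s = 0: 29.0 weeks on placebo, 42.3 on active;
- s = 6 (start of taper): 32.0 and 43.6 weeks.

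At a constant background rate, expected background events per patient are proportional to follow-up. The active/placebo ratio is 42.3/29.0 = 1.46 or 43.6/32.0 = 1.36 with no drug reaction at all. If AZD1419 does not delay loss of control, this imbalance does not arise.

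**The case against.** The strongest reply is that the SAP does not contradict the protocol. Section 6.1.1 ties the window to dose adaptation, and protocol 8.5.9.1 specifies no flu-like table. A wider safety table is therefore allowed, and the cross-reference could be read as bringing the window in. This stands in part. The text is not a plain contradiction, but the pair of tables in step 1 makes the imported-window reading hard to sustain. That inference is not proof, since the SAP uses the remainder period for all AEs; the IP-only table, however, appears in the flu-like paragraph.

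Other points on that side also stand:

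- The Week 6 and Week 9 cuts come from protocol 8.5.9.1.
- The dosing-period tables, the relatedness split and the placebo arm all help to isolate a reaction.
- Protocol 6.3.5 prefers diagnoses to symptom lists, so diagnosed influenza would normally not appear under the four terms.
- Late arthralgia is worth tabulating, given the autoimmune risk raised in protocol 1.3.
- Safety data are not formally tested and all data are listed.

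A reader might infer that seasonal illness will swamp the drug reaction. The documents give no rates to support this, and step 3 shows it only at a high background rate with a low reaction rate. A reader might also infer that the SAP wording affects dose adaptation. It cannot: investigators decide during the trial under protocol 4.2.2. Nor are flu-like events the only route to a lower dose, because 4.2 and 4.2.2 allow a reduction whenever a dose is judged not tolerated for any reason.

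**Conclusion.** The point holds as a defect in a reporting definition. The SAP cites a definition with a 24-hour window, does not write the window out, plans tables that imply it is not used, and does not log the departure. No flu-like table isolates events within 24 hours of a dose, and none separates doses 1-4 from doses 5-13.

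Firm from the documents: at most 13 of 365 days (3.6%) fall in the window for the during-study table and 4 of 302 (1.3%) for the remainder table, against 11-14% for the dosing-period tables.

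Dependent on assumptions: the amount of dilution, which ranges from modest to near-complete in the during-study table over the rates tried. The follow-up imbalance is 36-46% more expected background events on active if the plan's 20%/60% assumption and an exponential model hold. The error can therefore inflate as well as mask a drug signal. The primary analysis, sample size and dosing decisions are unaffected.

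**What to change.** In SAP 4.2.5.1:

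- Add a flu-like table restricted to the four terms with onset within 24 hours after an IP administration, derived from the recorded AE and IP dates and times.
- Show it for doses 1-4 and doses 5-13, with the number of doses given, because patients who lose control stop IP. Any display by assigned level should be labelled descriptive only, since level is selected on earlier tolerance.
- Give a convention for missing onset times, for example counting an event dated on the dosing day or the day after, and report how many events rest on it. SAP 3.4.1 covers missing onset dates but not time from dose.
- Keep the any-time period tables as supportive, stated to be without the window, and add exposure-adjusted rates for those running to Week 52.
- State that recorded maximum intensity may differ from the post-paracetamol grade used for adaptation.

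Record the change in SAP Section 6. The cost is one derived flag, one set of tables and a few lines of text, with no new data. The missing-time convention is slightly over-inclusive, because two calendar dates span more than 24 hours.
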